5.3.1.2 General Management of Sitravatinib Related Hematological Toxicities

Hematological toxicities are not a frequent cause of treatment interruption or discontinuation of sitravatinib treatment. Observed \geq Grade 3 hematological events that are considered to be causally related to sitravatinib should initially be managed using treatment interruption until resolution of toxicity to \leq Grade 2. In addition, dose reduction of sitravatinib will be implemented in the following cases:

- Grade 3 or 4 febrile neutropenia;
- Grade 4 neutropenia persisting for \geq 8 days; or
- Grade 4 thrombocytopenia of any duration or Grade 3 thrombocytopenia with bleeding.

Table 3: Dose Modifications for Sitravatinib Toxicity

Toxicity	Grade	Treatment Delay	Dose Modification
General non-hematologic toxicity ¹	1	Not required	None
	2	Not required	Asymptomatic: None required
			Symptomatic: None required. Early dose reduction to the next lower dose level is recommended over treatment interruption.
	3-4	Hold until \leq grade 1 or return to baseline	Resume at reduced dose. Exceptions presented in footnotes ²
Hematologic toxicities	1-2	Not required	None
	3	Hold until \leq grade 2	Reduce dose for grade 3 febrile neutropenia or grade 3 thrombocytopenia with bleeding
	4	Hold until \leq grade 2	Reduce for grade 4 febrile neutropenia, grade 4 neutropenia lasting \geq 8 days or grade 4 thrombocytopenia
Hypertension	1-2	Not required	None required
	3	Not clinically significant ³ : Not required	Decrease dose if unresponsive to anti-hypertensive treatment
		Clinically significant ³ : Hold until \leq grade 2 or return to baseline	Resume at decreased dose level
	4	Discontinue	Discontinue
Transaminitis	1	Not required	None required
	2	Not required	Decrease by one dose level
	3-4	Hold until \leq grade 1 or return to baseline	If resolution occurs within 29 days, decrease by 1 dose level. If no resolution within 29 days, discontinue sitravatinib

¹ Management of selected sitravatinib toxicities as per Section 5.3.2

² Patients may resume at the same dose in the following cases:

- a. Grade 3 or 4 electrolyte abnormality that is not clinically complicated and resolves spontaneously or with conventional medical treatment within 72 hours;

b. Grade 3 amylase or lipase elevation that is not associated with symptoms or other clinical (e.g., electrolyte abnormalities, radiographic changes) manifestations of pancreatitis.

³ Clinical significance is defined as either an increase of ≥ 30 mmHg in systolic BP to ≥ 180 mmHg or increase of ≥ 20 mmHg in diastolic BP to ≥ 110 mmHg, confirmed with repeated testing after at least 5 minutes

5.3.2 Management of Selected Sitravatinib Adverse Events

Hypertension

Hypertension, including Grade 4 events, has been reported with sitravatinib. Anti-hypertensive therapy should be considered for patients with Grade 3 hypertension without clinically significant increases in blood pressure (BP). In cases of Grade 3 hypertension with clinically significant increases in blood pressure (defined as either an increase of ≥ 30 mmHg in systolic BP to ≥ 180 mmHg or increase of ≥ 20 mmHg in diastolic BP to ≥ 110 mmHg, confirmed with repeated testing after at least 5 minutes), sitravatinib dosing will be temporarily suspended until blood pressure is controlled. Treatment with sitravatinib may then resume at the lower dose level (*Table 3*). If significant hypertension recurs, options include change in medical management of the patient, reduction of sitravatinib dose, or discontinuation of study treatment, at the discretion of the Treating Investigator. In the event of Grade 4 hypertension, sitravatinib will be permanently discontinued (*Table 3*)

Palmar-Plantar Erythrodysesthesia

Palmar plantar erythrodysesthesia (PPE) has been reported as a dose limiting toxicity in the Phase 1 study of sitravatinib. Measures that can be taken to manage PPE include avoidance of exposure of hands and feet to hot water when washing dishes or bathing, or to other sources of heat, avoidance of activities that cause unnecessary force or friction (rubbing) on the hands or feet, avoiding contact with harsh chemicals such as cleaning products, use of tools or household items that result in pressure on the hands, such as garden tools, knives, and screwdrivers, and wearing of loose fitting, well-ventilated shoes and clothes.

Treatment may include use of topical moisturizing agents, topical anesthetics, or topical anti-inflammatory medications such as corticosteroid creams. In more severe cases, dose interruption and reduction may be warranted.

Diarrhea

Diarrhea should be evaluated to determine whether it may be immune-mediated colitis due to pembrolizumab, related to sitravatinib, or due to another cause. Diarrhea has been reported with sitravatinib treatment, though the mechanism remains unclear. Patients should be counseled that diarrhea is a possible side effect and advised to take loperamide or a similar medication as needed if diarrhea due to sitravatinib develops. Any patients

developing dehydration or clinically significant electrolyte abnormalities due to sitravatinib should interrupt sitravatinib treatment, but treatment may be restarted once diarrhea is controlled. The diarrhea observed with sitravatinib generally improves within several days of interrupting study medication so discontinuation with close observation may help establish causality. If any features of the clinical presentation, including timing of presentation, failure to improve with dose interruption, laboratory or radiologic tests suggests the presence of immune-related colitis, all study medications should be withheld and treatment with immunosuppressive therapy considered as per Section 5.3.3.2.

Hemorrhagic Events

The risk of hemorrhagic events with sitravatinib has not been fully characterized, however, such events have been reported with inhibitors of VEGFR. Patients with active hemoptysis or gastrointestinal bleeding should not take sitravatinib and suspension of treatment is recommended for patients developing clinically significant bleeding.

Thrombotic Events

Arterial and venous thrombotic events have been observed with sitravatinib and described with other inhibitors of the VEGFR pathway. The majority of thrombotic events observed with sitravatinib have been venous thrombotic events. The occurrence of thrombotic events with sitravatinib is being monitored for further characterization. Patients with a history of VTE should be anticoagulated as per local standard of care. Treatment should be discontinued in subjects who develop clinically significant thromboembolic complications.

Thyroid Dysfunction Other than Immune-Related

Hypothyroidism and increases in thyroid-stimulating hormone (TSH) have been reported in patients taking sitravatinib. Patients diagnosed with hypothyroidism should be treated with thyroid replacement therapy and may continue treatment with sitravatinib.

Decreased Left Ventricular Ejection Fraction

Decreased LVEF has been reported with sitravatinib. In addition, decreases of LVEF to <50% on-study were observed in patients undergoing scheduled echocardiograms (ECHO) or multigated acquisition (MUGA) scans. The dose of sitravatinib should be interrupted and/or reduced in patients with an ejection fraction that has dropped $\geq 20\%$ below baseline and is <50%.. Discontinuation should be considered for patients requiring acute hospitalization for treatment of congestive heart failure (CHF).

Proteinuria

Proteinuria has been observed with sitravatinib and described with other inhibitors of the VEGFR pathway. Urinalysis for urine protein should be performed prior to each cycle following the start of sitravatinib and as clinically warranted during treatment with sitravatinib. Subjects who develop $\geq 2+$ proteinuria should undergo 24-hour urine collection for assessment of urine protein; treatment with sitravatinib should be discontinued in the presence of ≥ 2 grams of proteinuria/24 hours and may be restarted when protein levels decrease to less than 2 grams/24 hours. Subjects who develop nephrotic syndrome should be withdrawn from treatment with sitravatinib.

Increased Transaminases

The management of increases in AST and ALT should be guided by the clinical judgment of the Treating Investigator, including an assessment of the most likely causative etiology, with special consideration given to the potential for immune-related hepatitis. Increased transaminases should be evaluated to determine whether confounding factors exist, such as viral infection, metastatic lesions or biliary obstruction. Increased transaminases have been observed in subjects treated with sitravatinib. Most cases were asymptomatic elevations in ALT or AST, while some were associated with liver metastases or cholestasis. No cases of drug-induced liver injury meeting Hy's Law have been identified.

For cases where transaminase increases are not likely to be immune-related, treatment management decisions should be made using the Treating Investigator's discretion in consideration of clinical factors. Recommended treatment modifications for sitravatinib are provided in *Table 3*. However, if any features of the clinical presentation, including timing of presentation, failure to improve with dose interruption, laboratory or radiologic tests suggests the presence of immune-related hepatitis, all study medications will be withheld and treatment with immunosuppressive therapy considered as detailed in management of pembrolizumab related adverse events (Section 5.3.3)

Increased Amylase and Lipase

Increased amylase and lipase have been observed in subjects treated with sitravatinib and have been reported with other inhibitors of the VEGF pathway. Most sitravatinib-related treatment-emergent events of increased amylase and lipase were asymptomatic while some were associated with signs and/or symptoms of pancreatitis. Treatment with sitravatinib may continue without dose modification (eg, interruption or reduction) in cases of asymptomatic

amylase and/or lipase increases in the absence of other clinical evidence of pancreatitis (eg, symptoms, electrolyte abnormalities, radiographic changes) at the Treating Investigator's discretion. Sitravatinib should be interrupted for any grade pancreatitis and the subject managed according to standard-of-care. After resolution of pancreatitis, sitravatinib resumption is at the discretion of the Treating Investigator; if pancreatitis is assessed as sitravatinib treatment-related and treatment is resumed, a dose reduction is recommended.

Immune-Related Adverse Events (irAEs)

Single agent sitravatinib has not been associated with irAEs. However, the potential exists for irAEs associated with sitravatinib to contribute to irAEs associated with pembrolizumab treatment. In the event of a Grade 2 irAE during study treatment, administration of sitravatinib and pembrolizumab will be interrupted until the event stabilizes to Grade ≤ 1 (see Section 5.3.3 on pembrolizumab associated adverse event treatment). At the time of resumption of sitravatinib dosing, a dose reduction may be implemented at the discretion of the Treating Investigator.

Management of Grade 3 and 4 irAEs should be performed as in section on pembrolizumab related adverse events management (Section 5.3.3). Recurrent Grade 3, or any Grade 4, irAEs should generally be managed with permanent discontinuation of pembrolizumab, and temporary or permanent interruption of sitravatinib. Sitravatinib may be resumed at the same or lower dose at the discretion of the Treating Investigator once the event stabilizes to Grade ≤ 1 .

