5.2.3 Pembrolizumab Dose Modification or Discontinuation

Interruption or discontinuation of pembrolizumab may be required for some toxicities as summarized in *Table 2*. Treatment of suspected pembrolizumab related adverse events is discussed in Section 5.3.3. Dose reductions of pembrolizumab are not allowed. Dosing interruptions are permitted in the case of medical / surgical events or logistical reasons not

related to study therapy (e.g., elective surgery, unrelated medical events, patient vacation, and/or holidays). Subjects should be placed back on study therapy within 3 weeks of the scheduled interruption, unless otherwise discussed with the Sponsor Investigator. The reason for interruption should be documented in the patient's study record.

Table 2: Dose Modification Guidelines for Drug-Related Adverse Events for Pembrolizumab

Toxicity	Hold Treatment For Grade	Timing for Restarting Treatment	Discontinue Subject
Diarrhea/Colitis	2-3	Toxicity resolves to Grade 0-1.	Toxicity does not resolve within 12 weeks of last dose or inability to reduce corticosteroid to 10 mg or less of prednisone or equivalent per day within 12 weeks.
	4	Permanently discontinue	Permanently discontinue
AST, ALT, or Increased Bilirubin	2	Toxicity resolves to Grade 0-1	Toxicity does not resolve within 12 weeks of last dose.
	3-4	Permanently discontinue (see exception below) ¹	Permanently discontinue
Type 1 diabetes mellitus (if new onset) or Hyperglycemia	T1DM or 3-4	Hold pembrolizumab for new onset Type 1 diabetes mellitus or Grade 3-4 hyperglycemia associated with evidence of beta cell failure.	Resume pembrolizumab when patients are clinically and metabolically stable.
Hypophysitis	2	Toxicity resolves to Grade 0-1	Toxicity does not resolve within 12 weeks of last dose or inability to reduce corticosteroid to 10 mg or less of prednisone or equivalent per day within 12 weeks.
	3-4	Withhold until clinically stable or permanently discontinue depending on severity	Permanently discontinue depending on severity.
Hyperthyroidism	3-4	Withhold until clinically stable or permanently discontinue depending on severity	Toxicity does not resolve within 12 weeks of last dose or inability to reduce corticosteroid to 10 mg or less of prednisone or equivalent per day within 12 weeks.

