Hypothyroidism	2-4	Therapy with pembrolizumab can be continued while treatment for the thyroid disorder is instituted	Therapy with pembrolizumab can be continued while treatment for the thyroid disorder is instituted.
Infusion Reaction	3-4	Permanently discontinue	Permanently discontinue
Pneumonitis	2	Toxicity resolves to Grade 0-1	Toxicity does not resolve within 12 weeks of last dose or inability to reduce corticosteroid to 10 mg or less of prednisone or equivalent per day within 12 weeks.
	3-4	Permanently discontinue	Permanently discontinue
Renal Failure or Nephritis	2	Toxicity resolves to Grade 0-1	Toxicity does not resolve within 12 weeks of last dose or inability to reduce corticosteroid to 10 mg or less of prednisone or equivalent per day within 12 weeks.
	3-4	Permanently discontinue	Permanently discontinue

Toxicity	Hold Treatment For Grade	Timing for Restarting Treatment	Discontinue Subject
All Other Drug-Related Toxicity ²	3 or Severe	Toxicity resolves to Grade 0-1	Toxicity does not resolve within 12 weeks of last dose or inability to reduce corticosteroid to 10 mg or less of prednisone or equivalent per day within 12 weeks.
	4	Permanently discontinue	Permanently discontinue
Note: Permanently discontinue for any severe or Grade 3 drug-related AE that recurs or any life-threatening event.			
¹ For patients with liver metastasis who begin treatment with Grade 2 AST or ALT, if AST or ALT increases by greater than or equal to 50% relative to baseline and lasts for at least 1 week then patients should be discontinued. ² Patients with intolerable or persistent Grade 2 drug-related AE may hold study medication at physician discretion. Permanently discontinue study drug for persistent Grade 2 adverse reactions for which treatment with study drug has been held, that do not recover to Grade 0-1 within 12 weeks of the last dose.			

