5.3.3 Pembrolizumab-Related Adverse Events

5.3.3.1 General Management of Pembrolizumab-Related Adverse Events

Pembrolizumab related AE management is as per institutional standard of care, with the following recommended guidelines. Pembrolizumab must be withheld for certain drug-related toxicities and severe or life-threatening AEs as per *Table 2*. Subjects should receive appropriate supportive care measures as deemed necessary by the Treating Investigator. Suggested supportive care measures for the management of adverse events with potential immunologic etiology are outlined below. Where appropriate, these guidelines include the use of oral or intravenous treatment with corticosteroids as well as additional anti-inflammatory agents if symptoms do not improve with administration of corticosteroids. Note that several courses of steroid tapering may be necessary as symptoms may worsen when the steroid dose is decreased. These are guidelines and local standard of

care/institutional standards may be followed at the discretion of the Treating Investigator. For each disorder, attempts should be made to rule out other causes such as metastatic disease or bacterial or viral infection, which might require additional supportive care. The treatment guidelines are intended to be applied when the investigator determines the events to be irAEs. For guidelines regarding restarting pembrolizumab, please see *Table 2*.

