For Grade 2 events, hold pembrolizumab, treat with corticosteroids and provide hormonal supplementation as appropriate. When symptoms improve to Grade 1 or less, steroid taper should be started and continued over no less than 4 weeks. For Grade 3-4 events, treat with an initial dose of IV corticosteroids followed by oral corticosteroids. When symptoms improve to Grade 1 or less, steroid taper should be started and continued over no less than 4 weeks. Replacement of appropriate hormones may be required as the steroid dose is tapered.

Hyperthyroidism or Hypothyroidism:

Thyroid disorders can occur at any time during treatment. Monitor patients for changes in thyroid function (at the start of treatment, during treatment, and as indicated based on clinical evaluation) and for clinical signs and symptoms of thyroid disorders. For grade 2-4 hypothyroidism, thyroid hormone replacement therapy is indicated per standard of care. Pembrolizumab may be held if patients are severely symptomatic or show signs of myxedema. For Grade 2 hyperthyroidism, non-selective beta-blockers (e.g. propranolol) are suggested as initial therapy. For Grade 3-4 hyperthyroidism, hold pembrolizumab and consider treatment with corticosteroids in addition to treatment with non-selective beta-blockers. When symptoms improve to Grade 1 or less, steroid taper should be started and continued over no less than 4 weeks. Replacement of appropriate hormones may be required as the steroid dose is tapered.

Hepatitis:

For Grade 2 events, hold pembrolizumab and monitor liver function tests more frequently. Consider treatment with IV or oral corticosteroids if elevation persists for 3-5 days or if there are accompanying clinical symptoms. For Grade 3-4 events, hold pembrolizumab and treat with intravenous corticosteroids for 24 to 48 hours followed by high dose oral steroids. When symptoms improve to Grade 1 or less, a steroid taper should be started and continued over no less than 4 weeks.

Renal Failure or Nephritis:

For Grade 2 events, hold pembrolizumab and administer IV or oral corticosteroids. Consider nephrology consultation. For Grade 3-4 events, treat with IV corticosteroids. When symptoms improve to Grade 1 or less, steroid taper should be started and continued over no less than 4 weeks.

Management of Infusion Reactions:

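### Section 5.3.2 interrupts both drugs for any Grade 2 irAE, but Table 2 and Section 5.3.3.2 let pembrolizumab continue in Grade 2 hypothyroidism, and no text says which governs

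*Combined protocol and SAP*

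**What the plan says.** The general rule is in the paragraph on immune-related adverse events in Section 5.3.2: "In the event of a Grade 2 irAE during study treatment, administration of sitravatinib and pembrolizumab will be interrupted". The interruption lasts until the event is at Grade 1 or below. The sentence refers in parentheses to Section 5.3.3 for treatment of pembrolizumab-associated events and exempts no type of event.

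Section 5.3.3.1 sets the scope of the pembrolizumab guidance: "The treatment guidelines are intended to be applied when the investigator determines the events to be irAEs". It sends withholding to Table 2: "Pembrolizumab must be withheld for certain drug-related toxicities and severe or life-threatening AEs as per" that table.

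On hypothyroidism, Table 2 (Section 5.2.3) has one row for Grades 2-4. The grades stand in the column headed "Hold Treatment For Grade", but the text of the row reads: "Therapy with pembrolizumab can be continued while treatment for the thyroid disorder is instituted". Section 5.3.3.2 gives hormone replacement for the same grades and adds: "Pembrolizumab may be held if patients are severely symptomatic or show signs of myxedema".

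On hyperthyroidism, Table 2 has an entry only for Grade 3-4: "Withhold until clinically stable or permanently discontinue depending on severity". Section 5.3.3.2 suggests beta-blockers at Grade 2 and mentions holding pembrolizumab only at Grade 3-4.

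Section 5.1.3 links the two drugs: an event that requires pembrolizumab to be interrupted also interrupts sitravatinib. For irAEs it sends the reader to Section 5.3.1.

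**The concern.** An investigator with a patient who has Grade 2 immune-related hypothyroidism finds two answers. Section 5.3.2 stops both drugs. Table 2 and Section 5.3.3.2 allow pembrolizumab to continue. Each answer can be defended from a stated passage, and the trial may run at up to 2 sites, so the same event could be handled in two ways.

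The issue bears on patient management, because it decides whether treatment stops for this event. It also bears on how compliance is judged: a monitor who works from Section 5.3.2 could record a deviation where the investigator followed Table 2. The situation is foreseeable, since the study calendars schedule thyroid testing at screening, at Cycle 3, at every other cycle after that, and at end of treatment.

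**Working it through.** No arithmetic applies. The check is whether the passages reach the same event, whether they give different actions, and whether any text ranks them.

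**Step 1: same event.** Section 5.3.2 covers any Grade 2 irAE. Section 5.3.3.1 applies its guidelines to events that the investigator judges to be irAEs. Grade 2 hypothyroidism judged to be immune-related therefore falls under both.

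**Step 2: actions side by side.**

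| Text | Grade 2 immune-related hypothyroidism | Grade 2 immune-related hyperthyroidism |
|---|---|---|
| Section 5.3.2, irAE paragraph | Interrupt sitravatinib and pembrolizumab | Interrupt sitravatinib and pembrolizumab |
| Table 2, Section 5.2.3 | Pembrolizumab may go on; grade printed in the hold column | No Grade 2 entry |
| Section 5.3.3.2 | Hormone replacement; hold optional, if severe symptoms or myxedema | Beta-blocker suggested; nothing on a hold |

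For hypothyroidism, a mandatory interruption meets an express permission to continue. For hyperthyroidism, a mandatory interruption meets silence.

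**Step 3: the Table 2 row itself.** The column heading says treatment is held at the grades listed, and the row lists 2-4. The row text says treatment can go on. The row is unclear even without Section 5.3.2.

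**Step 4: is there an exception elsewhere?** Section 5.3.2 has a thyroid paragraph under which sitravatinib may continue in hypothyroidism. Its heading is "Thyroid Dysfunction Other than Immune-Related", so it does not reach the immune-related event.

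**Step 5: is there a ranking?** Sections 5.1.3, 5.2.3, 5.3.2, 5.3.3.1 and 5.3.3.2 contain no statement that the Grade 2 rule or Table 2 prevails. The reference from 5.3.2 to 5.3.3 leads to the differing text without ranking it. The next paragraph of 5.3.2 offers a contrast: for Grade 3 and 4 irAEs it hands management over to Section 5.3.3. The Grade 2 sentence states its own action.

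**Step 6: sitravatinib.** Section 5.1.3 follows whatever the pembrolizumab rule requires. If Section 5.3.2 governs, sitravatinib is interrupted too. If Table 2 governs, Section 5.1.3 by itself triggers no sitravatinib interruption, yet Section 5.3.2 still names sitravatinib directly. The uncertainty therefore covers both drugs.

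**The case against.** The strongest answer is that the texts can all be obeyed together. Table 2 and Section 5.3.3.2 give permissions and do not forbid an interruption, so an investigator who stops both drugs breaches nothing. Section 5.3.2 also points to Section 5.3.3, which points to Table 2, and 5.3.3.1 leaves room for institutional standards at the Treating Investigator's discretion. A reader could conclude that the event-specific table sets the pembrolizumab hold.

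Much of this stands. The passages are connected, and this is a mandate against a permission, which is milder than two instructions that cannot both be followed. What remains is that an investigator who uses the permission breaches Section 5.3.2. The discretion in 5.3.3.1 is over the 5.3.3 guidelines and does not mention the 5.3.2 rule.

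A reader might infer more than the documents support:

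- **That Grade 2 hyperthyroidism is an equal contradiction.** Table 2 and Section 5.3.3.2 are silent on a Grade 2 hold and give no instruction to continue. A suggested beta-blocker is compatible with interruption.
- **That one reading stops both drugs and the other stops neither.** Section 5.1.3 is triggered by whichever pembrolizumab rule applies, so it cannot be counted on the side of Table 2.
- **That the conflict extends to irAEs not listed by organ.** Footnote 2 of Table 2 gives discretion over intolerable or persistent Grade 2 drug-related events in general and does not mention irAEs. Section 5.3.2 can be read as the narrower rule beside it.
- **That Grade 2 colitis is a further case.** Section 5.3.3.2 adds a 3-day condition that Table 2 lacks, but 5.3.3.1 makes the Table 2 holds mandatory and calls the 5.3.3.2 measures guidelines. That largely settles it.

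**Conclusion.** The point holds in a limited form. For Grade 2 immune-related hypothyroidism, Section 5.3.2 requires both drugs to be interrupted, Table 2 and Section 5.3.3.2 permit pembrolizumab to continue, and no text says which prevails. The hypothyroidism row of Table 2 also disagrees with its own column heading. Grade 2 hyperthyroidism is a gap to close in the same edit, not a second contradiction.

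The size is one event at one grade, for two drugs. The documents give no rate for it under this combination, so no number of patients is claimed. Nothing here changes the response-rate design, its error rates or its power. The conclusion assumes that the event has been judged immune-related; otherwise the Section 5.3.2 irAE rule does not apply.

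**What to change.** The sponsor should reconcile the irAE paragraph of Section 5.3.2 with Table 2 and Section 5.3.3.2, as follows:

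- State one action for each drug in Grade 2 immune-related hypothyroidism.
- Make the hypothyroidism row of Table 2 agree with its hold-grade column.
- State whether the Section 5.3.2 rule or Table 2 governs when they differ, including for Grade 2 hyperthyroidism.
- As an editorial point, correct the reference in Section 5.1.3: it sends the reader to 5.3.1 for irAEs, but that text is in 5.3.2.

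Which action applies is for the sponsor's clinical leads to decide. The cost is a protocol wording amendment, with no added visits or tests.
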